10.1. Sample Size Determination

The sample size for the study was chosen to provide sufficient data to evaluate the primary objective of this study and is not intended to achieve any a priori statistical requirements.

Approximately 49 Japanese patients with T2DM may be enrolled so that approximately 32 patients complete the study with compliant defined dosing regimen. The estimated drop-out rates are 30% for Cohorts 1 and 3 and 50% for Cohort 2. Patients will be administered 8 weekly SC doses of LY3298176 or placebo in a ratio of 12 LY3298176:3 placebo for Cohorts 1 and 3, and 16 LY3298176:3 placebo for Cohort 2. Considering the possibility of higher drop-out rate when administered the highest dose level of LY3298176, the number of patients to be enrolled in Cohort 2 is higher than those for the other 2 cohorts.

Replacement of discontinued patients is not planned because the sample size is determined considering the expected drop-out rate.

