9.4.2 Pharmacodynamic Statistical Methodology

Statistical inference on PD parameters (fasting blood glucose, OGTT glucose, and insulin) will be based on the patients who are included in the PD population. PD parameters may be transformed before statistical analyses, if deemed necessary.

The observed results, as well as change from baseline, will be analyzed by treatment regimen, using mixed-effects models to evaluate treatment effects, as well as treatment comparisons. The model will include treatment regimen actually received, as a fixed effect and the patient as a random effect. For repeated measured parameters, day and treatment regimen-by-day interaction terms will be included in the model. Baseline (Day -1) values, as well as other influencing variables, may be used as covariates. An unstructured covariance structure will be applied. If the model fails to converge, alternative structures shall be examined using Akaike's criteria. The main comparisons will be between each LY3298176-treated group and placebo group. Least-squares means as well as 95% CIs will be reported.

Example SAS code for repeated measures analysis:

```
proc mixed data=pd;
  class subject trtreg day;
  model chg = base trtreg day trtreg*day / residual ddfm=kr;
  repeated day / subject=subject type=un;
  lsmeans trtreg / alpha=0.05 cl pdiff;
  ods output lsmeans=lsm;
  ods output diffs=diff;
run;
```

where 'chg' is the change from baseline, 'base' is the baseline value, and 'trtreg' is the treatment regimen.

Example SAS code for mixed-effects analysis:

```
proc mixed data=pd;
  class subject trtreg;
  model pd = trtreg / residual ddfm=kr;
  random subject;
  lsmeans trtreg / alpha=0.05 cl pdiff;
  ods output lsmeans=lsm;
  ods output diffs=diff;
run;
```

where 'trtreg' is the treatment regimen.

The individual observed and mean (SD) time profile of the postdose PD parameters will be plotted by treatment regimen. Additional exploratory analyses of PD parameters may be performed to understand dose response using relevant model considering titration scheme, as deemed appropriate.

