9.5.5 Electrocardiogram (ECG)

The ECG data will be obtained directly from the 12-lead ECG traces. These data include the PR, QT, QTcB intervals, QRS duration and heart rate, where QTcB is the QT interval corrected using Bazett's formula. In addition, QTcF (the QT interval corrected using Fridericia's formula) will be calculated as follows:

$$QTcF = \frac{QT}{\sqrt[3]{(60/HR)}}$$

The ECG data will be summarized by treatment regimen together with changes from baseline, where baseline is defined as the mean of all measurements on Day 1 predose of the treatment period. Figures of mean ECG data and mean changes from baseline will be presented by treatment regimen.

A plasma LY3298176 concentration-QT analysis will be performed to assess the changes from baseline (Day 1 predose) and placebo in the (double delta) QTcF interval relative to plasma LY3298176 concentrations across all active treatments. The change from baseline adjustment will be based on individual subject's Day 1 predose value, and the change from placebo adjustment will be based on the mean of time-matched placebo values.

Further details on how these will be calculated:

- Calculate the arithmetic mean of the triplicate QTcF for each subject at each timepoint and use this in all subsequent calculations below.
- Calculate the change from baseline at each timepoint for each individual subject who received LY3298176.
- Calculate the mean change from baseline across all the placebo subjects at each timepoint.

- For each subject that received LY3298176 at each corresponding timepoint subtract the mean placebo change from their own individual change from baseline.
- BLQ LY3298176 concentration data will be imputed to 50% of the LLOQ for the purposes of the analysis.

The analysis will be performed by plotting double delta QTcF against LY3298176 concentrations, including all post Day 1 dosing timepoints.

A mixed effects analysis model will be performed on the double delta QTcF values and will include LY3298176 concentration as a covariate and subject as a random effect. The results of the model and associated 90% CI will be fitted on the plot and the p-value for the slope reported. Estimated double delta QTcF and 90% CI at the geometric mean C_{max} will also be presented.

Additional analysis to evaluate effects of AE (such as gastrointestinal or hypoglycemia events) QTcF may be performed if deemed necessary.

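### The concentration-QTcF model in SAP 9.5.5 has no patient-specific slope, so its standard error is too small if patients differ; adding one helps only if the placebo data are modelled too

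*SAP*

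**What the plan says.** SAP 9.5.5 plans a concentration-QT analysis over all active treatments, "including all post Day 1 dosing timepoints". The response is double-delta QTcF: each active patient's change from the Day 1 predose value, minus a placebo term, where "the change from placebo adjustment will be based on the mean of time-matched placebo values". The model "will include LY3298176 concentration as a covariate and subject as a random effect". The outputs are a fitted line with a 90% CI, "the p-value for the slope reported", and the following: "Estimated double delta QTcF and 90% CI at the geometric mean C_{max} will also be presented".

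Section 9.5.5 gives no code, covariance structure, degrees-of-freedom method or robust standard error for this model, and it mentions no random slope. Elsewhere the SAP codes a patient effect in two ways. The mixed-effects example in 9.4.2 uses "random subject", which is an intercept only. The repeated-measures examples in 9.4.2 and 9.5.4 use an unstructured within-patient covariance, which the accompanying text names explicitly. Section 9.5.5 names no such structure, so the intercept-only form is the ordinary reading.

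Protocol 10.3.1.2 treats concentration-response work on QTcF as exploratory and optional. Neither document attaches an alpha, threshold or decision rule to it.

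**The concern.** Each active patient contributes many visits, and in Cohorts 1 and 2 the dose, and so the concentration, rises with calendar time. A patient who is more or less QTcF-sensitive than average departs from the common line in proportion to concentration. A patient whose QTcF drifts slowly for other reasons departs in much the same way. A random intercept absorbs a constant offset but not a departure that grows with concentration. The model then treats that departure as visit-to-visit noise and understates the uncertainty of the mean slope.

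The slope p-value and the CI at Cmax are the only inferential QT results that the SAP commits to; the other ECG outputs are descriptive. Too small a standard error can make a slope look established, or an upper bound look lower than the data support. The issue is separate from error in the subtracted placebo mean and would remain if that mean were known exactly.

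**Working it through.** **Inputs from the documents.** Protocol 10.1 sets the allocation at "12 LY3298176:3 placebo for Cohorts 1 and 3, and 16 LY3298176:3 placebo for Cohort 2".
- Enrolled: 15 + 19 + 15 = 49, as stated.
- Completers at 30%/50%/30% drop-out: 15×0.7 + 19×0.5 + 15×0.7 = 30.5, against about 32 stated.
- Active patients: 12 + 16 + 12 = 40. Placebo: 3 + 3 + 3 = 9.
- Paired post-dose triplicate-ECG and PK times to Day 64 (Schedule of Activities): Day 1 at 8, 24, 48 and 72 h; predose on Days 8, 15, 22, 29, 36, 43 and 50; Day 50 at 8, 24 and 168 h; Day 64. That is 15 per patient and 40×15 = 600 points.
- Half-life about 5 days, peak at 1–2 days (Protocol 3.2).

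The documents state no alpha, power or variance for this test, so there is no QT figure to reproduce.

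**Formula.** Suppose y_ij = a + (b + s_i)C_ij + u_i + e_ij, with patient slopes s_i of mean 0 and SD τ. The intercept-only fit weights patients by their concentration spread (weights w_i). Its slope still has mean b, but

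Var(b̂) ≈ V_model + τ²·Σw_i²,

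and the reported standard error reflects essentially only the first term.

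**Set-up A (assumed values).** True mean slope 0, no placebo-mean error, no drop-out; intercept SD 7 ms, residual SD 6–8 ms (7 ms for drift), half-life 120 h, 25% exposure variability. Slope SD is in ms at the Cohort 2 peak. Ranges span the residual SDs and repeated runs, most of 1,000 or 1,500 trials per scenario.

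| Slope SD | Rejection at nominal 5% | Coverage of 90% CI at Cohort 2 peak |
|---|---|---|
| 0 | 4–5% | – |
| 3 ms | 6–8% | about 89% |
| 5 ms | 9–16% | 82–85% |
| 8 ms | 18–25% | 75–78% |

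- Patient drift with no drug relation: 7–9% rejection at SD 5 ms, 15–16% at 8 ms.
- Random concentration slope: 3–7% rejection, 87–92% coverage.
- Patient-clustered standard errors: 4–7% rejection, about 88–91% coverage.
- With the stated drop-out: intercept-only 11–12% (SD 5 ms) and 16–23% (SD 8 ms); clustered 6–9%.
- Correction widens the 90% half-width by about 0.2–0.9 ms. A separate run put the rise in the upper bound at 0.1 ms (SD 3), about 0.4 ms (SD 5) and 0.9–1.0 ms (SD 8).

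**Set-up B (assumed values).** Intercept SD 5 ms, residual SD 5 or 8 ms, 30% exposure variability, peak at about 41 h, no drop-out; 1,000 trials each. Slope SD is in ms at the 10-mg-regimen Cmax. The simulated Cohort 2 peak is 1.43 times that, so 2, 4 and 6 ms correspond to 2.9, 5.7 and 8.6 ms on set-up A's scale.

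| Slope SD | Intercept only, residual 5 / 8 | Random slope, residual 5 / 8 |
|---|---|---|
| 0 | 6.3 / 5.8% | 4.4 / 4.0% |
| 1 | 5.6 / 4.2% | 4.7 / 3.0% |
| 2 | 8.3 / 7.2% | 4.3 / 4.9% |
| 4 | 21.0 / 15.1% | 5.6 / 6.4% |
| 6 | 34.7 / 20.4% | 5.8 / 6.6% |

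Monte Carlo error is about 0.7 points near 5%.

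**Check of the mechanism (residual SD 5).** The mean reported SE is 0.69, 0.71 and 0.73 at slope SD 0, 4 and 6. The actual SD of the estimate is 0.72, 1.13 and 1.53.
- Slope SD 4: 1.96×0.71/1.13 = 1.23, a two-sided tail of 22% (simulated 21.0%).
- Slope SD 6: 1.96×0.73/1.53 = 0.94, a tail of 35% (simulated 34.7%).
- The extra variance gives Σw_i² = (1.13² − 0.72²)/4² = 0.047 and (1.53² − 0.72²)/6² = 0.051. The slope is thus replicated over roughly 1/0.05 = 20 effective patients.

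**Adding the placebo subtraction that 9.5.5 requires.** In set-up B, with the 9-patient mean subtracted and no slope in any patient, the intercept-only model rejects 32% of the time at nominal 5%. With a random slope it still rejects 21–32% across scenarios. A further run gave 26–34% with 57–59% coverage of the 90% CI. Clustered standard errors gave 21–35% and 53–67%.

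**The case against.** The strongest case against has four parts.

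1. *The text is under-specified rather than wrong.* Section 9.5.5 has no code, and the intercept-only reading is borrowed from a model without a concentration term. This stands as a caution, but nothing in 9.5.5 points to a random slope or an unstructured covariance.
2. *The effect in milliseconds is small and rests on an assumed SD.* This stands. At a slope SD of 1 ms at the 10-mg-regimen Cmax there is no visible inflation. The larger rejection rates need a mean slope of zero with patient slopes of SD 5–8 ms at the peak, so some patients shorten while others prolong. A drug with no QTcF effect in any patient, and no drift, is the SD 0 row, where the test is close to nominal.
3. *Nothing depends on it.* The analysis is exploratory and no test level is set. Protocol 10.3.1.2 also plans patient-level QTcF categories. This lowers the priority; it does not make the standard error right.
4. *A random slope does not rescue the planned analysis.* This stands and changes the fix.

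A reader might infer that the p-value tests whether any patient has a slope. It does not: the coefficient estimates the mean slope, and only its standard error fails. A reader might also infer that 600 points are treated as fully independent. The random intercept already absorbs a constant patient offset; with intercept and residual SDs both 7 ms, the implied within-patient correlation is 49/(49 + 49) = 0.5. What it misses is the part that grows with concentration.

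**Conclusion.** The point holds as a cheap improvement to an exploratory analysis. As ordinarily read, 9.5.5 fits one common slope with a random intercept. Its slope p-value and the 90% CI at the geometric mean Cmax are then too optimistic to a degree set by how much patients differ or drift. Under set-up A, rejection at a nominal 5% runs from about 4–5% with no differences to 18–25% at a slope SD of 8 ms, and the CI half-width is short by about 0.2–0.9 ms. The documents supply none of these variances, and the headline figures set placebo-mean error to zero and ignore drop-out.

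A reader might conclude that a random slope brings the planned test to its nominal level. It does so only when the placebo mean carries no error. As 9.5.5 is written, every active patient has the same 9-patient mean subtracted at each timepoint, and the p-value and CI stay invalid until that is also addressed.

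**What to change.** In SAP 9.5.5, model change-from-baseline QTcF instead of double-delta values. Include the placebo patients with concentration set to zero, and use fixed effects for treatment (active or placebo), nominal timepoint and concentration. Protocol 9.5.1 does not plan assays of placebo samples, so setting these to zero needs no new data.

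Replace the single subject effect with `random intercept conc / subject=subject type=un`, using Kenward-Roger degrees of freedom. If that does not converge, keep the random intercept and use patient-clustered (empirical) standard errors. Take the slope p-value from this model. Take the placebo-corrected estimate and 90% CI at the geometric mean Cmax as the treatment effect plus slope times Cmax.

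The cost is a few lines of text and code. The downsides are a slightly wider CI when patients differ and possible non-convergence under the expected drop-out, which the fallback covers. The combined model was not simulated here. The random-slope runs in set-up B used N−1 degrees of freedom, not Kenward-Roger. Clustered errors ran slightly high (6–9%) under drop-out, which is why they are the fallback and not the first choice.

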5.5. Justification for Dose

The doses of LY3298176 in this study are selected to provide a full evaluation of the safety, tolerability, PK, and PD of LY3298176 in Japanese patients with T2DM to support dose selection in future clinical trials in patients with T2DM in Japan. The dose of LY3298176 for Cohort 1 is titrated from 2.5 mg to 10 mg—2.5 mg for Days 1 and 8; followed by 5 mg for Days 15 and 22; and then 10 mg for Days 29, 36, 43, and 50. The dose of LY3298176 for Cohort 2 is titrated from 5 mg to 15 mg—5 mg for Days 1 and 8; followed by 10 mg for Days 15, 22, 29, and 36; and then 15 mg for Days 43 and 50. The dose of LY3298176 for Cohort 3 is a fixed

5-mg weekly dose for 8 weeks. The anticipated dose-limiting safety and tolerability of LY3298176 are GI-related AEs, such as nausea and vomiting (Section 3.2), which have been consistently demonstrated with the GLP-1 drug class.

The planned dose levels of LY3298176 were selected on the basis of the following:

- Safety and tolerability of LY3298176 in healthy subjects and patients with T2DM in the Phase 1 Study GPGA through doses of up to 15 mg (Section 3.2). In Study GPGA, using a rapid titration scheme of 5 mg, 5 mg, 10 mg, and 15 mg, the dose of 15 mg was considered safe but not well tolerated. It is expected that a more gradual titration method is needed to reach 15 mg with better tolerability; hence, this study will explore getting to the highest dose of 15 mg via a longer titration during 8 weeks.
- The dose-titration regimen starting at 2.5 mg and 5 mg in Cohorts 1 and 2, respectively, are based on tolerability modelling and intended to reduce GI-related AEs.
- The 10-mg and 15-mg doses for Cohorts 1 and 2, respectively, will provide information on safety, tolerability, PK, and PD around expected maximum tolerated dose levels in the up-titration regimen.
- The fixed 5-mg dose in Cohort 3 is to compare safety, tolerability, PK, and PD profiles of LY3298176 in this study with that of Study GPGA (first cohort of Part C).

6. Study Population

Eligibility of patients for study enrollment will be based on the results of screening medical history, physical examination, medical assessment, vital signs, clinical laboratory tests, and ECG.

A chest x-ray will be completed at screening unless one has been obtained within the past 12 months, and the x-ray and/or report are available for review.

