10.3.1.2. Statistical Evaluation of Safety

Safety parameters that will be assessed include safety laboratory parameters, vital signs, ECG parameters, injection-site reactions, and hypoglycemia. The parameters will be listed and summarized using standard descriptive statistics.

Laboratory measurements will be summarized with respect to observed values and change from baseline by treatment group at each time point using descriptive statistics. In addition, all clinical chemistry, hematology, and urinalysis data outside the reference ranges will be tabulated by parameter and treatment group.

Vital signs will be summarized with respect to observed values and change from baseline (Day 1, Predose) by treatment at each time point using descriptive statistics. For change from baseline values, a mixed-model repeated-measure model with treatment, time (of measurement), and treatment-by-time interaction as fixed effects, patient as random effect, and baseline as covariate will be used to determine the effects of LY3298176.

Electrocardiogram parameters, including the pulse rate, QT interval, RR interval, and QTc using Fridericia's formula (QTcF), QRS interval duration, and heart rate, will be summarized. The number and percentage of patients with a maximum increase from baseline in QTcF will be summarized for each treatment group according to the following categories: >30 milliseconds and >60 milliseconds. In addition, the number and percentage of patients with QTcF postdose values according to the following categories: >450 milliseconds, >480 milliseconds, and >500 milliseconds, will be summarized by treatment group. Exploratory analyses may be performed to determine the effects of LY3298176 concentration-response analysis of QTcF.

Additional analysis will be performed, if warranted, upon review of the data.

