9.3.2 Pharmacokinetic Statistical Methodology

PK parameters will be summarized using descriptive statistics by dose level.

PK dose proportionality may be assessed in an exploratory manner in model-based analysis performed by Eli Lilly.

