9.5.4 Vital signs

Vital signs data will be summarized by treatment regimen together with changes from baseline, where baseline is defined as Day 1, predose. Figures of mean vital signs and mean changes from baseline profiles will be presented by treatment regimen. Furthermore, values for individual patients will be listed.

For change from baseline in vital signs, a mixed-model repeated-measure model with treatment regimen, time (of measurement), and treatment regimen-by-time interaction as fixed effects, patient as random effect, and baseline as covariate will be used to determine the effects of LY3298176. An unstructured covariance structure will be applied. If the model fails to converge, alternative structures shall be examined using Akaike's criteria. Least-squares means, as well as 95% CIs, will be reported.

Example SAS code:

```
proc mixed data=safety;
  class subject trtreg day;
  model chg=trtreg day trtreg*day base / residual ddfm=kr;
  repeated day / subject=subject type=un;
  lsmeans trtreg*day / alpha=0.05 cl pdiff;
  ods output lsmeans=lsmeans;
  ods output diff=diffs;
run;
```

where 'chg' is the change from baseline, 'base' is the baseline value, and 'trtreg' is the treatment regimen.

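### SAP 9.5.5 does not say which geometric mean Cmax the QTcF estimate is read at, so a tabulated estimate at the top exposure is not assured; the same model omits baseline QTcF

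*SAP*

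**What the plan says.** SAP 9.5.5 subtracts each patient's Day 1 predose QTcF and then the mean placebo change at the same timepoint. It models the resulting double delta QTcF "relative to plasma LY3298176 concentrations across all active treatments", using all timepoints after Day 1 dosing. The model terms it names are concentration as a covariate and subject as a random effect.

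Two outputs follow. The first is graphical: "The results of the model and associated 90% CI will be fitted on the plot and the p-value for the slope reported". The second is numerical: "Estimated double delta QTcF and 90% CI at the geometric mean" Cmax. The numerical output comes with no dose level, regimen or day.

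Three other places bear on this:

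- SAP 9.5.5 also states that "The ECG data will be summarized by treatment regimen together with changes from baseline", with figures of the means. The 5 mg to 15 mg regimen is a separate group in SAP section 6.
- SAP 9.3.2 states that "PK parameters will be summarized using descriptive statistics by dose level". Protocol 10.3.2.2 has the same summaries by dosing regimen.
- The vital-signs change-from-baseline model in SAP 9.5.4 has treatment regimen, time, their interaction, "and baseline as covariate will be used to determine the effects of LY3298176". The repeated-measures example code in SAP 9.4.2 also carries a baseline term.

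**The concern.** The sentence uses one singular geometric mean Cmax after a model that spans all active treatments. Full PK profiles are taken after doses 1 and 8 in each of three regimens (Protocol section 2, PK sampling footnote), so it could refer to any of six geometric means or to some pool of them. A programmer cannot tell which, and the choice could be made after the data are seen.

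The choice matters because the exposures differ about tenfold. Protocol 5.5 says that the 10 mg and 15 mg doses "will provide information on safety, tolerability, PK, and PD around expected maximum tolerated dose levels in the up-titration regimen". That sentence is about dose selection and not about QT, but it shows that the top exposures are a purpose of the design. With a rising line, an estimate read at mid-range is smaller than one read at the top. Its CI is also narrower, because mid-range lies nearer the centre of the observed concentrations.

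The second part concerns precision. Every change from baseline carries the error in that patient's baseline. The Day 1 predose baseline averages many tracings (Protocol 9.4.3), but all come from one day, so the patient's deviation on that day remains. A baseline covariate removes part of it, and the model as stated does not use one.

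**Working it through.** The documents give no figure for this point, so there is none to reproduce. The check asks how far a pooled geometric mean Cmax would lie below the 15 mg Day 50 peak.

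**Inputs from the documents**

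- Weekly doses (Protocol 5.1). Cohort 1: 2.5, 2.5, 5, 5, 10, 10, 10, 10 mg. Cohort 2: 5, 5, 10, 10, 10, 10, 15, 15 mg. Cohort 3: 5 mg eight times.
- Active patients 12, 16 and 12; dropout 30%, 50% and 30% (SAP section 7). Active completers: 12 × 0.7 = 8.4, 16 × 0.5 = 8, 12 × 0.7 = 8.4, in total 24.8.
- Half-life about 5 days (range 109 to 123 h), peak at 1 to 2 days, PK linear and dose proportional (Protocol 3.2).

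**Assumptions**

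One compartment with first-order absorption; every patient follows the planned titration; equal geometric CV in all groups (which leaves the ratios unchanged).

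**Step 1: Cmax by regimen and day**

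Concentration is the sum over doses *i* (numbered from 0) of dose × ka/(ka − ke) × [exp(−ke·u) − exp(−ka·u)], where u = t − 168·i hours since that dose. Here ke = ln 2 / half-life, and ka is solved from tmax = ln(ka/ke)/(ka − ke). At a half-life of 120 h and tmax of 36 h, relative to the Cohort 2 Day 50 peak:

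| Regimen | Day 1 | Day 50 |
|---|---|---|
| 2.5 to 10 mg | 0.105 | 0.695 |
| 5 to 15 mg | 0.21 | 1.00 |
| 5 mg fixed | 0.21 | 0.352 |

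Over half-lives of 109 to 123 h and tmax of 24 to 48 h, these move only to 0.10-0.11, 0.20-0.22, 0.69-0.70 and 0.35.

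**Step 2: pooled geometric means**

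The formula is exp(Σ n·ln r / Σ n), where r is the relative Cmax.

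- Day 50, completers: (8.4·ln 0.695 + 8·ln 1 + 8.4·ln 0.352)/24.8 = (−3.06 + 0 − 8.77)/24.8 = −0.477, giving **0.62**.
- Day 1, all enrolled: (12·ln 0.105 + 28·ln 0.21)/40 = (−27.05 − 43.70)/40 = −1.769, giving 0.17.
- Days 1 and 50 together: (−70.75 − 11.83)/64.8 = −1.274, giving **0.28**.

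Without dropout, the Day 50 value is 65-66% and the two days together give 33-34%.

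**Step 3: effect on a reported estimate**

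Suppose the line reaches 10 ms at the 15 mg peak.

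- Zero intercept: 10 × 0.28 = 2.8 ms and 10 × 0.62 = 6.2 ms.
- Assumed intercept of 3 ms, so a slope contribution of 7 ms: 3 + 7 × 0.28 = 5.0 ms and 3 + 7 × 0.62 = 7.3 ms.

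The SAP does not remove the intercept, so the first pair is only a limiting case.

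**Step 4: baseline covariate**

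The documents give no QTcF variances. The assumed ranges are a between-patient SD of 12-20 ms and a day-to-day SD of 5-9 ms. The share of patient-level variance in change that a baseline term can remove is day² / (between² + day²). That is 25/(400 + 25) = 6% at one end and 81/(144 + 81) = 36% at the other. The standard error of the estimate falls by much less, because within-patient noise and slope uncertainty remain. Simulating 40 active and 9 placebo patients at 15 ECG times gives a reduction of roughly 0-10%.

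**The case against.** A reader might infer that the QT effect at 15 mg would not be reported at all. The documents do not support that. The fitted line and its 90% CI are drawn over the full concentration range, which includes the 15 mg concentrations, and ECG changes are summarized and plotted for the 5 mg to 15 mg regimen. What could be missing is a tabulated model estimate at that exposure.

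A reader might also take pooling as the plan. It is one reading only. The reference to all active treatments describes the data entering the model, and SAP 9.3.2 summarizes PK by dose level, which would give 15 mg its own geometric mean. Nothing suggests averaging first-dose and eighth-dose Cmax, so the 28% belongs to the less likely pooled reading. Nor is an estimate at a stated lower concentration wrong; it is correct for that concentration. Protocol 10.3.1.2 makes the concentration-QTcF analysis exploratory and optional.

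All of this stands, and it limits the point to an unspecified reading point. It does not remove it:

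- SAP 9.5.5 does not refer to SAP 9.3.2, which names no day and groups differently from Protocol 10.3.2.2.
- The by-regimen ECG summaries are not placebo-corrected, and the standard statistics in SAP 9.1 include no CI.
- The 5 mg to 15 mg regimen may contain patients who were held at a lower dose.
- The protocol's QTcF counts, "according to the following categories: >30 milliseconds and >60 milliseconds", do not appear in SAP 9.5.5. The SAP states that it supersedes the protocol's statistical considerations (section 3) and limits summaries to those it details (section 9.1).

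On the baseline term, the text of SAP 9.4.2 says only that baseline may be used, and its second code example has none. The precedent is therefore partial, and the gain could be close to zero.

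**Conclusion.** The point holds as a specification gap with a small precision point attached. SAP 9.5.5 leaves open which geometric mean Cmax is used, and a tabulated double delta QTcF estimate at the top exposure is not assured. If Cmax is pooled, the reading point is about 62% (Day 50) or 28% (Days 1 and 50) of the 15 mg Day 50 peak. Those figures rest on dose-proportional PK, a half-life of about 5 days, planned titration and the planned dropout. If the sponsor intends a value per dose level, the shortfall disappears and only the wording is at issue.

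The matter is worth settling because this model supplies the only placebo-corrected QTcF estimate with a CI that the SAP specifies, in a study whose primary objective is safety. The missing baseline term is secondary: a reduction in standard error of roughly 0-10%, resting on SDs that are assumed and not documented.

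**What to change.** Replace the sentence on the estimate in SAP 9.5.5 with wording such as: *Estimated double delta QTcF and 90% CI will be presented at the Day 50 geometric mean Cmax of each regimen, and at the Day 50 geometric mean Cmax of the patients who received the highest dose given on that day.* The last clause keeps patients who were not up-titrated from lowering the top reading point, and it still works if the Cohort 2 regimen is changed as the protocol allows.

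In the same model, add baseline QTcF as a covariate, centred on the placebo mean baseline so that the estimate corresponds to the placebo group whose mean change is subtracted.

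Both are SAP wording and programming changes. The baseline and PK data are already collected. The downside is that the CI at the top exposure is wider than at a pooled Cmax, and few patients may reach the highest dose (about 8 active completers are expected in Cohort 2).
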